#### Amendments

No.	Date
1	Ver 1.0 2018-03-08
2	Ver 2.0 2019-01-10
3	Ver 3.0 2020-01-10
4	Ver 4.0 2021-02-08
5	Ver 5.0 2022-05-10

## List of Abbreviations and Definitions of Terms

Abbreviation	Definition
AE	Adverse event
ALT	Alanine aminotransferase
ALP	Alkaline phosphatase
ANC	Absolute neutrophil count
AST	Aspartate transaminase
aPTT	activated partial thromboplastin time
Bil	Total bilirubin
CBC	Complete blood count
Ccr	Creatinine clearance
CR	Complete response
Cru	Complete response/unconfirmed
CRF	Case report form
CSF	Cerebrospinal fluid
CT	Computed tomography
D/C	Differential count
DCR	Disease control rate
DOH	Department of Health
ECG	Electrocardiogram
FDA	Food and Drug Administration
GCP	Good clinical practice
G-CSF	Granulocyte colony-stimulating factor
Gr	Grade
IHC	Immunohistochemical stain
IRB	Institutional Review Board
ITT	Intent to treat
IVF	Intravenous infusion
LVEF	Left ventricular ejection fraction
MRI	Magnetic resonance imaging
NCI-CTCAE	National Cancer Institute Common Terminology Criteria for Adverse Events
NCTRC	National Clinical Trial and Research Center,
NS	0.9% Normal saline

NTUH	National Taiwan University Hospital
NYHA	New York Heart Association
ORR	Objective response rate
OS	Overall survival
PD	Progressive disease
PFS	Progression-free survival
PI	Principal investigator
PO	Per os
PR	Partial response
RECIST	Response evaluation criteria in solid tumor
SAE	Serious adverse event
SD	Stable disease
SPD	Sum of the products of the greatest diameter
WBC	White blood cell
WOCBP	Women of childbearing potential
UNL	upper normal limit

## Synopsis

Title of Study	A single-arm phase Ib/II study of the combination of lenvatinib and eribulin in advanced adipocytic sarcoma and leiomyosarcoma (LEADER study)
Rationale of Study	
Recently, the US Food and Drug Administration (FDA) granted approval to eribulin for the treatment of adipocytic sarcoma who have received a prior anthracycline-containing regimen based on a Phase III study results of improved overall survival (OS) as compared with the standard treatment dacarbazine. In the leiomyosarcoma cohort of the study, although eribulin did not demonstrate a significant benefit over dacarbazine, still about 5.1% of leiomyosarcoma patients treated with eribulin had a partial response, suggesting that eribulin may have activity against leiomyosarcoma. However, the overall response rate (ORR) and progression-free survival (PFS) remained unsatisfactory in the two most common soft tissue sarcoma (STS) subtypes—adipocytic sarcoma and leiomyosarcoma, prompting new therapeutic options of STS patients.
 
Anti-angiogenic therapies had shown promising results in soft tissue sarcoma (ST). Pazopanib, an anti-angiogenic multi-kinase inhibitor, has shown clinical benefit with a longer median PFS of 4.6 months versus placebo in STS patients refractory to at least one line of systemic chemotherapy. Another anti-angiogenic targeted therapy, regorafenib, showed significant improvement in PFS as compared with placebo in various STS. In a phase I study of lenvatinib for solid tumors in Japan, 4 out of 6 leiomyosarcoma patients has tumor decreased more than 10%. Moreover, other tyrosine receptor targets of lenvatinib, such as fibroblast growth factor receptor (FGFR) and platelet-derived growth factor receptor (PDGFR), may also plays a role in treating STS. In high-grade STS patients, about 30% of patients had FGFR1 amplification or overexpression. FGFR1-overexpression STS cell lines are sensitive to FGFR inhibitors such as BGJ398 and AZD4547. Furthermore, a monoclonal antibody of PDGFR alpha, olaratumab, was recently approved by the FDA in combination with doxorubicin for advanced STS based on a median 10-month OS benefit compared to doxorubicin only in a randomized phase II trial.
 
It has been demonstrated in various cancer types that an increased

[figure not shown]
	
quantity of tumor infiltrating lymphocyte (TILs) is associated with increased response to chemotherapy or improved prognosis. One of the factors that had been shown to impede the migration and trafficking of TILs into tumor is vascular endothelial growth factor (VEGF). In renal cell carcinoma, treatment with bevacizumab, an anti-VEGF antibody, or in combination with atezolizumab, increased the recognition of tumor antigen, increased expression of MHC class I receptor on tumor cells, and the amount of TIL migration into the tumor stroma. Many of the STS were detected with scarce TILs in the tumor microenvironment ([name] et al. unpublished data), thus it would be interesting to see if anti-angiogenic tyrosine kinase inhibitors could adjust the tumor microenvironment toward a more chemotherapy-friendly milieu.
 
Thus, we would like to propose a clinical trial to understand the anti-tumor activity of the combination of lenvatinib and eribulin in advanced STS patients.

Objectives and Endpoints
	
Primary objective To evaluate the anti-tumor activity of lenvatinib and eribulin combination in STS.
 
Primary endpoint for phase Ib The safety profile of the combination of lenvatinib and eribulin
 
Primary endpoint for phase II The objective response rate (ORR) based on RECIST 1.1.
 
Secondary objectives and endpoints
 
 
● 24-week progression-free survival (PFS) rate
 
● 6- and 12-months overall survival (OS) rate
 
● PFS
 
● OS
 
● Safety profile of the combination of lenvatinib and eribulin
 

Study Design
	
Open-label single arm phase Ib/II study

Schema	
 
The diagram illustrates the treatment schedule. Lenvatinib (18mg/day) is administered daily from Day 1 to Day 21 of each cycle. Eribulin (1.1 mg/m²) is administered on Day 1 and Day 8 of each cycle. The schedule shows cycles C1D1, C1D8, C1D15, and C2D1. Tumor assessment is performed at the end of each cycle. Biopsies are conducted before C1D1 and after tumor assessment.
 
 
Study Treatment:
 
A 21 day cycle
 
Table 1: Dose levels of lenvatinib and eribulin combination
 
  
 Dose level	Lenvatinib	Eribulin	
   
 Dose level 11	18mg/day D1-D21	1.1 mg/m^2 D1, D8	
 
 Dose level 21	14mg/day D1-D21	1.1 mg/m^2 D1, D8	
 
 Dose level 31	10mg/day D1-D21	1.1 mg/m^2 D1, D8	
 
 Dose level 12	18mg/day D1-D21	0.7 mg/m^2 D1, D8	
 
 Dose level 22	14 mg/da D1-D21	0.7 mg/m^2 D1, D8	
  
 
The first 6 patients will be treated with lenvatinib 18 mg/day D1-D21 and eribulin 1.1mg/m^2 D1 and D8 (Dose level 11). If no more than 2 (≤ 2) patients had dose-limiting toxicity (DLT) in the first cycle (3 weeks), then the lenvatinib (18) and eribulin (1.1) combination will be declared safe. If more than 2 (> 2) patients have DLT, the investigators will determine which drug is more pertain to the DLT(s) and then will follow the customized block chart to shift the dose. If lenvatinib is determined to be related to DLT, the next lower dose would be dose level 21. Otherwise, if eribulin is determined to be the likely cause for DLT, the next dose level will be level 12. The lowest dose acceptable would be ether dose level 22 or dose level 31. If still more than 2 patients have DLT in the first 6 patients of dose level 22 or level 31, the combination of lenvatinib and eribulin will be considered too toxic in STS patients.
 
Both agents will be continued until disease progression or intolerable toxicity.
	Dose level	Lenvatinib	Eribulin	Dose level 11	18mg/day D1-D21	1.1 mg/m  D1, D8	Dose level 21	14mg/day D1-D21	1.1 mg/m  D1, D8	Dose level 31	10mg/day D1-D21	1.1 mg/m  D1, D8	Dose level 12	18mg/day D1-D21	0.7 mg/m  D1, D8	Dose level 22	14 mg/da D1-D21	0.7 mg/m  D1, D8
Dose level	Lenvatinib	Eribulin																	
Dose level 11	18mg/day D1-D21	1.1 mg/m  D1, D8																	
Dose level 21	14mg/day D1-D21	1.1 mg/m  D1, D8																	
Dose level 31	10mg/day D1-D21	1.1 mg/m  D1, D8																	
Dose level 12	18mg/day D1-D21	0.7 mg/m  D1, D8																	
Dose level 22	14 mg/da D1-D21	0.7 mg/m  D1, D8																	
Sample Size (according to primary endpoint)	
The study will be based on a minimax Simon 2 stage design. The ORR of interest with lenvatinib and eribulin combination is 20% (P1), and the ORR of low interest is set at 5% (P0). With an 80% power and type I error of 0.05, if no patients had an objective response to lenvatinib
																		

	and eribulin combination after the first 13 enrollments, the trial will be stopped early for futility. If at least one patient had an objective response, the study will continue to include 27 evaluable patients. With an expected 10% drop-out rate, we estimate a total of 30 patients to be enrolled in this study
Study Sites	Single nation, multi-center
Criteria for Inclusion and Exclusion	
Inclusion criteria
 
To be eligible for inclusion, patients must fulfill the following criteria:
 
 
1. A histological confirmed adipocytic sarcoma (dedifferentiated, myxoid, or pleomorphic) or leiomyosarcoma that is either inoperable locally advanced or metastatic
 
2. Advanced adipocytic sarcoma and leiomyosarcoma who have received no more than 2 lines of systemic chemotherapy in the advanced setting (not including adjuvant chemotherapy).
 
3. At least one measurable tumor according to RECIST 1.1. If the measurable lesion has previously received radiotherapy, the tumor must be a progressive lesion after radiotherapy.
 
4. ECOG PS 0 or 1 or Karnofsky performance status (KPS) <math>\geq</math> 70
 
5. Patients must have adequate organ function and marrow reserve measured within 14 days prior to randomization as defined below: 
 
■ Hemoglobin <math>\geq</math> 9.0 g/dL;
 
■ Absolute neutrophil count <math>\geq</math> 1,500 / L;
 
■ Platelets <math>\geq</math> 75,000/ L;
 
■ Total bilirubin <math>\leq</math> 1.5 x upper normal limit;
 
■ AST(SGOT)/ALT(SGPT) <math>\leq</math> 2.5 x upper normal limit; for patients with liver metastases AST(SGOT)/ALT(SGPT) <math>\leq</math> 5 x upper normal limit is allowed;
 
■ Serum creatinine <math>\leq</math> 1.5mg/dL or creatinine clearance <math>\geq</math> 50ml/min;
 
■ aPTT <math><</math> 1.5 x upper normal limit (unless on therapeutic anti-coagulation);
 
■ Proteinuria <math>\leq</math> 1+ with urine dipstick, if <math>></math> 1+, 24-hour urine protein must be <math>\leq</math> 1 g
 
 
 
6. Age 20 or older.
 
7. Patient's life expectancy is more than 3 months
 
8. All women of childbearing potential must have a negative pregnancy test obtained within 72 hours before starting
 

	
therapy.
 

9. Patients with reproductive potential must use effective contraception (hormone or barrier method of birth control; abstinence) prior to study entry, for the duration of study participation, and for 6 months after the completion of therapy.

10. Patient needs to have adequate wash-out period from previous systemic treatment(s):

(1) 2 weeks for any other oral anti-cancer targeted agents

(2) 3 weeks for any other cytotoxic chemotherapy (except for mitomycin-C, which will require 6 weeks)

(3) 3 weeks for monoclonal antibodies, including immune checkpoint inhibitors

 
Exclusion criteria
 
Patients who fulfill any of the following criteria will be excluded from this trial:
 

1. Patients who had received lenvatinib or eribulin treatment

2. Patients who had leptomeningeal metastasis, either diagnosed by brain imaging study or confirmed by cerebrospinal fluid cytology examination (patients with brain metastasis that are under control is eligible).

3. Patients with clinical signs or symptoms of gastrointestinal obstruction and who require parenteral hydration and/or nutrition because of obstruction.

4. Patients with uncontrollable hypertension (defined as systolic blood pressure over 140mmHg and/or diastolic pressure over 90mmHg despite anti-hypertensive medications)

5. Patients with the following cardiac disease

-Prolongation of corrected QT (QTc) interval to >480 milliseconds (ms).

-Significant cardiovascular impairment: history of

(a) congestive heart failure greater than New York Heart Association Class II;

(b) unstable angina;

(c) myocardial infarction;

(d) stroke or transient ischemic attack; or

(e) cardiac arrhythmia associated with hemodynamic instability within 6 months of the first dose of study drugs.

6. Bleeding subjects at risk for severe hemorrhage.

--	--

	
 
7. Major surgical procedure, open biopsy, or significant traumatic injury within 28 days prior to enrollment.
 
8. History of allergic reaction to compounds of similar chemical composition to the study drugs
 
9. Pregnancy or lactation.
 
10. Patients with latent HBV (positive HBsAg or HBeAg) or HCV infection (positive anti-HCV antibody)
 

Study Medication
	
Lenvatinib 18mg/day, D1-D21 PO  Eribulin 1.1 mg/m^2 D1, D8 IVF  Every cycle is 21 days  (The above listed dose is the expected dose, but the final starting dose will be determined in the phase Ib part)
 
Figure 1. Dose adjustment directions by DLT
  
When a safe combination dose is determined, this dose would become the initial dose for the following patients. Dose adjustment for study drugs for adverse events that occur after cycle 1 should follow the protocol guidelines.

	
DLT is defined as
 
 
(1) Grade 4 diarrhea
 
(2) Grade 3 or higher proteinuria
 
(3) Grade 3 or higher hand foot syndrome
 
(4) Grade 3 or 4 peripheral neuropathy
 
(5) Neutropenia Grade 4 that lasted >5 days
 
(6) Neutropenia Grade 3 or 4 complicated by fever and/or infection (Absolute Neutrophil Count [ANC] < 1.0 x 10^9/L, fever ≥38.5°C)
 
(7) Thrombocytopenia Grade 4 of any duration
 
(8) Thrombocytopenia Grade 3 complicated by bleeding and/or which required platelet or blood transfusion
 
(9) Other Grade 3 or 4 clinically significant non-hematologic toxicities (except for inadequately treated nausea and/or vomiting) considered related to study drug
 
(10) Failure to administer ≥ 75% of the planned dosage of combination therapy as a result of treatment related (at least possibly related) toxicity during Cycle 1.
 
(11) Grade 3 or above hypertension not able to be controlled by medication
 
(12) Grade 3 or above gastrointestinal perforation
 
(13) Grade 4 hemorrhage
 
(14) Grade 3 thromboembolic event
 
(15) Grade 3 or above wound dehiscence requiring medical or surgical intervention
 


Therapeutic Assessments
	
 
1. Therapeutic assessment by CT or MRI will be performed from week 8, 16, and 24 and then every 12 weeks afterwards. A +/- 3 days window is allowed.
 
2. Biopsy will be performed at baseline and after the first tumor assessment (optional)
 

# 1 Introduction

## Background

Recently, the US Food and Drug Administration (FDA) granted approval to eribulin for the treatment of adipocytic sarcoma who have received a prior anthracycline-containing regimen based on a Phase III study results of improved overall survival (OS) as compared with the standard treatment dacarbazine. In the leiomyosarcoma cohort of the study, although eribulin did not demonstrate a significant benefit over dacarbazine, still about 5.1% of leiomyosarcoma patients treated with eribulin had a partial response, suggesting that eribulin may have activity against leiomyosarcoma [1]. However, the overall response rate (ORR) and progression-free survival (PFS) remained unsatisfactory in the two most common soft tissue sarcoma (STS) subtypes—adipocytic sarcoma and leiomyosarcoma, prompting new therapeutic options of STS patients.

Anti-angiogenic therapies had shown promising results in soft tissue sarcoma (ST). Pazopanib, an anti-angiogenic multi-kinase inhibitor, has shown clinical benefit with a longer median PFS of 4.6 months versus placebo in STS patients refractory to at least one line of systemic chemotherapy [2]. Another anti-angiogenic targeted therapy, regorafenib, showed significant improvement in PFS as compared with placebo in various STS [3]. In a phase I study of lenvatinib for solid tumors in Japan, 4 out of 6 leiomyosarcoma patients has tumor decreased more than 10% [4]. Moreover, other tyrosine receptor targets of lenvatinib, such as fibroblast growth factor receptor (FGFR) and platelet-derived growth factor receptor (PDGFR), may also plays a role in treating STS. In high-grade STS patients, about 30% of patients had FGFR1 amplification or overexpression. FGFR1-overexpression STS cell lines are sensitive to FGFR inhibitors such as BGJ398 and AZD4547 [5]. Furthermore, a monoclonal antibody of PDGFR alpha, olaratumab, was recently approved by the FDA in combination with doxorubicin for advanced STS based on a median 10-month OS benefit compared to doxorubicin only in a randomized phase II trial [6].

It has been demonstrated in various cancer types that an increased quantity of tumor infiltrating lymphocyte (TILs) is associated with increased response to chemotherapy or improved prognosis [7]. One of the factors that had been shown to impede the migration and trafficking of TILs into tumor is vascular endothelial growth factor (VEGF) [8]. In renal cell carcinoma, treatment with bevacizumab, an anti-VEGF antibody, or in combination with atezolizumab, increased the recognition of tumor antigen, increased expression of MHC class I receptor on tumor cells, and the amount of TIL migration into the tumor stroma [9]. Many of the STS were detected with scarce TILs in the tumor microenvironment ([name] et al. unpublished data), thus it would be interesting

to see if anti-angiogenic tyrosine kinase inhibitors could adjust the tumor microenvironment toward a more chemotherapy-friendly milieu.

Thus, we would like to propose a clinical trial to understand the anti-tumor activity of the combination of lenvatinib and eribulin in advanced STS patients.

## 2 Objectives and Endpoints

Objectives and related endpoints are described in Table 1 below.

Table 1 Objectives and related endpoints

Objectives	Endpoints	Definition and analysis
Primary (phase Ib)		
To evaluate the safety of lenvatinib and eribulin combination in STS	Dose limiting toxicities (DLT)	Refer to section 5.3
Primary (phase II)		
To evaluate anti-tumor activity of lenvatinib and eribulin combination in STS	Objective Response Rate (ORR)	Refer to Section 7.1
Secondary (phase II)		Refer to Section 7.2
To evaluate the disease control ability of lenvatinib and eribulin in STS	(Progression-free survival) PFS rate at 24- weeks	Refer to Section 7.2.1
	Overall survival rate at 6- and 12-months	Refer to Section 7.2.2
	PFS and OS	Refer to Section 7.2.3
To evaluate the safety dose combination of lenvatinib and eribulin in STS	Incidence, type, intensity, severity and seriousness of Adverse Events (AEs) and frequency of dose interruptions	Refer to section 7.2.4
To evaluate anti-tumor activity of lenvatinib and eribulin combination in STS using other assessment method	Objective Response Rate (ORR) by Choi criteria	Refer to section 7.2.5

## 3 Patient Selection Criteria

### 3.1 Inclusion criteria

To be eligible for inclusion, patients must fulfill the following criteria:

1. A histological confirmed adipocytic sarcoma (dedifferentiated, myxoid, or pleomorphic) or leiomyosarcoma that is either inoperable locally advanced or metastatic
2. Advanced adipocytic sarcoma and leiomyosarcoma who have received no more than 2 lines of systemic chemotherapy in the advanced setting (not including adjuvant chemotherapy)
3. At least one measurable tumor according to RECIST 1.1. If the measurable lesion has previously received radiotherapy, the tumor must be a progressive lesion after radiotherapy.
4. ECOG PS 0 or 1 or Karnofsky performance status (KPS)  $\geq$  70
5. Patients must have adequate organ function and marrow reserve measured within 14 days prior to randomization as defined below:
  - Hemoglobin  $\geq$  9.0 g/dL;
  - Absolute neutrophil count  $\geq$  1,500 / $\mu$ L;
  - Platelets  $\geq$  75,000/ $\mu$ L;
  - Total bilirubin  $\leq$  1.5 x upper normal limit;
  - AST(SGOT)/ALT(SGPT)  $\leq$  2.5 x upper normal limit; for patients with liver metastases AST(SGOT)/ALT(SGPT)  $\leq$  5 x upper normal limit is allowed;
  - Serum creatinine  $\leq$  1.5mg/dL or creatinine clearance  $\geq$  50ml/min;
  - aPTT  $<$  1.5 x upper normal limit (unless on therapeutic anti-coagulation);
  - Proteinuria  $\leq$  1+ with urine dipstick, if  $>$  1+, 24-hour urine protein must be  $\leq$  1 g
6. Age 20 or older.
7. Patient's life expectancy is more than 3 months
8. All women of childbearing potential must have a negative pregnancy test obtained within 72 hours before starting therapy.
9. Patients with reproductive potential must use effective contraception (hormone or barrier method of birth control; abstinence) prior to study entry, for the duration of study participation, and for 6 months after the completion of therapy.
10. Patient needs to have adequate wash-out period from previous systemic treatment(s):
  - (1) 2 weeks for any other oral anti-cancer targeted agents
  - (2) 3 weeks for any other cytotoxic chemotherapy (except for mitomycin-C, which will require 6 weeks)
  - (3) 3 weeks for monoclonal antibodies, including immune checkpoint inhibitors

### 3.2 Exclusion criteria

Patients who fulfill any of the following criteria will be excluded from this trial:

1. Patients who had received lenvatinib or eribulin treatment
2. Patients who had leptomeningeal metastasis, either diagnosed by brain imaging

- study or confirmed by cerebrospinal fluid cytology examination (patients with brain metastasis that are under control is eligible).
3. Patients with clinical signs or symptoms of gastrointestinal obstruction and who require parenteral hydration and/or nutrition because of obstruction.
  4. Patients with uncontrollable hypertension (defined as systolic blood pressure over 140mmHg and/or diastolic pressure over 90mmHg despite anti-hypertensive medications)
  5. Patients with the following cardiac disease
    - Prolongation of corrected QT (QTc) interval to >480 milliseconds (ms).
    - Significant cardiovascular impairment: history of
      - (a) congestive heart failure greater than New York Heart Association Class II;
      - (b) unstable angina;
      - (c) myocardial infarction;
      - (d) stroke or transient ischemic attack; or
      - (e) cardiac arrhythmia associated with hemodynamic instability within 6 months of the first dose of study drugs.
  6. Bleeding subjects at risk for severe hemorrhage.
  7. Major surgical procedure, open biopsy, or significant traumatic injury within 28 days prior to enrollment.
  8. History of allergic reaction to compounds of similar chemical composition to the study drugs
  9. Pregnancy or lactation.
  10. Patients with latent HBV (positive HBsAg or HBeAg) or HCV infection (positive anti-HCV antibody)

## **4 Study Design**

### **4.1 Overall plan of the study**

This is a single country multi-center, open-label phase Ib/II single-arm study in advanced adipocytic and leiomyosarcoma patients. Patients will be treated with the combination of lenvatinib and eribulin until disease progression, intolerable toxicity, or patient withdrawal.

The first 6 patients will be enrolled in a phase Ib run-in period to evaluate the safety of the combination of lenvatinib and eribulin. If more than 2 patients experience dose-limiting toxicity(s), dose adjustments will be carried out according to a pre-determined plan. If there are still more than 2 patients in the lowest pre-specified dose of combination, the combination would be declared too toxic for further treatment in STS patients.

## 4.2 Study schema

(Please refer to Figure 1)

## 4.3 Study period and end of study

- Expected recruitment rate: 1 patient/ month
- Expected enrollment duration of the study: 24 months
- Expected follow-up period: 12 months after the last patient accrual.
- Proposed extension of study timeline to 2022/12/13 for complete recruitment, follow-up, and analysis
- Expected total patient accrual: 30 patients
- End of study:
  - This will be a 2-stage study design based on the method proposed by Simon et al. The first stage will recruit 13 patients including 6 patients in the phase Ib part. If 0 patients had any objective response, the study will be unlikely to meet the pre-determined endpoint, and thus will be terminated early. If one or more patients had objective response, a total of 30 patients could be recruited.
  - The study may also terminate early if the combination is too toxic, i.e. that there are more than 2 patients met the DLT criteria in the lowest pre-determined combination dose (detail see Figure 2) in phase Ib part.

[figure not shown]

Figure 1. The schema of the study

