## **8 Statistical Considerations**

### **8.1 Sample size**

The study will be based on a minimax Simon 2 stage design. The ORR of interest with lenvatinib and eribulin combination is 20% (P1), and the ORR of low interest is set at 5% (P0). With an 80% power and type I error of 0.05, if no patients had an objective response to lenvatinib and eribulin combination after the first 13 enrollments, the trial will be stopped early for futility. If at least one patient had an objective response, the study will continue to include 27 evaluable patients. With an expected 10% drop-out rate, we estimate a total of 30 patients to be enrolled in this study.

If no dose de-escalation is needed in the phase Ib part, the 6 patients will be considered eligible to be included in the phase II part statistical analysis. If a lower dose is selected as the dose to go forward, only patients with the same dose as the phase II part will be included in the phase II statistical part.

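### Section 4.3's accrual rate and duration give 24 patients, not 30, and its end date allows the promised 12-month follow-up only if the last patient entered by 13 December 2021

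*Combined protocol and SAP*

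**What the plan says.** Section 4.3 of the protocol sets out the study period as a list. It gives a rate ("Expected recruitment rate: 1 patient/ month"), a duration ("Expected enrollment duration of the study: 24 months"), a total ("Expected total patient accrual: 30 patients") and a follow-up commitment ("Expected follow-up period: 12 months after the last patient accrual"). It then adds a calendar date: "Proposed extension of study timeline to 2022/12/13 for complete recruitment, follow-up, and analysis". No revised rate, revised duration, first-patient date or last-entry date goes with that extension.

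The phase Ib patients are counted inside the total: "The first stage will recruit 13 patients including 6 patients in the phase Ib part". Section 8.1 reaches the 30 by another route. If stage 1 passes, "the study will continue to include 27 evaluable patients", and a 10% drop-out allowance is added.

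The amendment list ends with "Ver 5.0 2022-05-10".

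**The concern.** Rate, duration and total cannot all be right, and the promised follow-up may not fit before the end date. A reader cannot tell from section 4.3 how long the trial was meant to run.

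The practical stake is in the secondary endpoints. Section 7.2.1 (24-week PFS rate) and section 7.2.2 (6- and 12-month OS rates) are written as the percentage of patients without an event by the time point. Neither says how to count a patient whose follow-up stops earlier, and section 8.2.1 offers only descriptive statistics and confidence intervals. Counting such a patient as event-free biases the rate upward. Dropping those still alive with short follow-up, while keeping those who died early, biases it downward. Whether this arises depends on when the last patients entered relative to the end date.

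**Working it through.** **Inputs.** Section 4.3: 1 patient per month; 24 months of enrolment; 30 patients; 12 months of follow-up after the last entry; end date 13 December 2022. Section 8.1: P0 = 5%, P1 = 20%, type I error 0.05, power 80%, stop at 0 responses in 13, 27 evaluable, 10% drop-out. Amendment list: version 1.0 on 8 March 2018, version 5.0 on 10 May 2022.

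**Step 1: is the 30 sound?** An exact search for the minimax two-stage design (one-sided 0.05 assumed, since the sidedness is not stated) returns 0/13 and 3/27, with type I error 0.0416 and power 0.801. This matches the plan's 13 and 27. Drop-out: 27 / (1 − 0.10) = 30. The total is correct, so the fault lies in the rate or the duration.

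**Step 2: rate × duration.**
- 1 × 24 = 24 patients. 30 − 24 = 6 short (20%); 27 − 24 = 3 short of the evaluable number.
- Counting a first patient at month 0 gives 25, still short of both.
- Duration needed at the stated rate: 30 / 1 = 30 months.
- Rate needed for the stated duration: 30 / 24 = 1.25 per month.
- Total with follow-up: 30 + 12 = 42 months, against 24 + 12 = 36 as listed.

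**Step 3: end date against follow-up.**
- 13 December 2022 − 12 months = 13 December 2021, the latest entry that allows 12 months of follow-up. Any time kept for analysis moves it earlier.
- 13 December 2022 − 42 months = 13 June 2019, the latest start of enrolment for the full plan at 1 per month.
- Version 1.0 to the end date is 57.2 months; less 12 for follow-up leaves 45.2, so a 30-month enrolment could fit.

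**Step 4: which endpoints could be cut short.** A patient entering after 13 December 2021 has no 12-month survival status at the end date unless already dead. The same applies to the 6-month status for entry after about 13 June 2022 (183 days back), and to week 24 for entry after 28 June 2022 (168 days back).

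**The case against.** Rate, duration and total are all labelled as expectations, and the 24-month line may be an early estimate left in place when the extension was added. That is plausible, but the conflicting lines still stand in one list of the current text.

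It could be argued that 24 patients plus 6 from phase Ib make 30. The text does not allow this: the duration is for the study as a whole, and the 6 sit inside the first 13.

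A reader might infer that the primary test loses power. If accrual closed at 24 months, power would be 73% with all 24 evaluable, or 66% with 22 (24 × 0.9 = 21.6). These figures take success as 4 or more responses, a cut-off the protocol does not print. But nothing closes accrual at 24 months. Sections 4.3 and 8.1 govern it by patient number, and the extension is itself meant to complete recruitment. The loss is hypothetical.

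A reader might also infer from the version 5.0 date that recruitment was still open in May 2022, leaving those entrants at most 217 days (7.1 months). The documents do not show this. They give no enrolment dates and do not say which version added the extension line, which may have been carried forward. The date is also called proposed, so it should not be treated as immovable, though it is the only end date given.

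Finally, section 7.2.3 already censors PFS and OS for patients without an event. That covers the time-to-event analyses but not the fixed-time rates, which are separately defined as percentages.

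**Conclusion.** The inconsistency is real and needs no assumption: the stated rate and duration give 24 patients against 30 expected and 27 evaluable. The listed timeline is 6 months too short at the stated rate (36 against 42 months), or the rate is 20% too low for the stated duration (1 against 1.25 per month).

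The end date and the 12-month follow-up are compatible only if the last patient entered by 13 December 2021, or earlier with time for analysis. Whether that happened cannot be told from the documents, so the effect on the 12-month OS rate is conditional on late entry; the effect on the 6-month OS and 24-week PFS rates needs later entry still.

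The response-rate design stands as long as accrual runs to the patient number. This is a planning and reporting defect that should be corrected, with no demonstrated effect on the primary endpoint.

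**What to change.** 1. In section 4.3, restate the enrolment duration as 30 months at 1 patient per month, or the rate as 1.25 per month over 24 months. Keep accrual governed by the 30 enrolled.
2. Either define the end of study as 12 months after the last entry, or keep 13 December 2022 and state the last-entry date it implies, 13 December 2021.
3. In sections 7.2.1 and 7.2.2, estimate the 24-week PFS and the 6- and 12-month OS rates by Kaplan-Meier, with confidence intervals, censoring patients whose follow-up is shorter. This assumes that late entrants have a similar prognosis to earlier ones.

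I would not replace the enrolment target with a rule that closes accrual once 27 patients count for the primary endpoint. Section 8.1 leaves out phase Ib patients treated at a dose other than the phase II dose, and drop-out could exceed 10% (at an assumed 15%, 27 / 0.85 = 31.8, so 32), so that rule could need more than 30 patients.

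**Cost.** Wording only, with no change to the planned 30. The stated timeline grows by about 6 months at the stated rate. If the end is tied to the last entry and entry was late, the study could run up to 12 months past 13 December 2022.
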